# 6.7 Concomitant Medications and Therapies

All administered concomitant medications (including herbal supplements) and non-medicinal therapies (including transfusions) used 28 days prior to Cycle One Day One, and until 30 days after the last dose of study therapy will be recorded in the subject's research chart and corresponding eCRF. All medications, including those used to treat adverse events, chronic conditions or diseases, or as supportive therapy should be documented in the eCRF.

### 6.7.1 Prohibited Therapy

Medications or vaccinations specifically prohibited in the exclusion criteria are not allowed during the active treatment period (Refer to Appendix 5). Subjects are prohibited from receiving the following therapies during the treatment phase of this trial:

- Anti-cancer systemic chemotherapy or biological therapy;
- Other investigational agents;
  - Exception: therapies given for the prevention, treatment or management of COVID-19 under the FDA emergency use authorization are allowed.
- Radiation therapy >10 Gy to any one lesion;
- Any live-attenuated vaccine therapies for the prevention of infectious disease (e.g. MMR, or rotavirus);
  - Exception: Vaccines for the prevention of COVID-19 are allowed.
- Herbal remedies known to potentially interfere with major organ function (e.g. hypericin);
- Strong P-glycoprotein inhibitors (P-gp);
- Breast Cancer Resistance Protein (BCRP) inhibitors;
- Strong CYP3A4 inhibitors and/or inducers.

If a subject requires treatment with one or more of the listed prohibited medications, the subject may need to be taken off study therapy. Each case will be considered and if possible, the investigator should discuss with the DSMC and Medical Monitor prior to initiating prohibited therapy.

#### 6.8 Recommended Infectious Prophylaxis

The use of infectious prophylaxis medications are strongly recommended given the immunocompromised state of CLL patients and potential for leukopenia/neutropenia while being treated with RP-3500 and olaparib. While prophylaxis regimens can be determined by the treating

provider and according to institutional guidelines, Table 15 summarizes the recommended regimens for infectious prophylaxis and appropriate alternatives. If the patient is allergic to all of the medications listed for each specific type of infection, then an infectious disease physician should be consulted for help in management.

G-CSF administration and formulation are as per institutional standard.

Table 15. Recommended infection prophylaxis medications.

Prophylaxis	Preferred Medication	Alternative Medication	Duration	
Viral				

Herpes Simplex

Varicella Zoster

	Acyclovir* 400mg to 800mg PO BID	Valacyclovir* 500mg to 1000mg PO daily	Entirety of treatment and trial	
Bacterial (if neutropenia with ANC <1,000/µL is expected to last ≥7 days)	
 
G-CSF administration is strongly recommended
 
Levofloxacin* 500mg PO/IV daily
 
	
 
G-CSF administration is strongly recommended
 
Cefpoxodime* 200mg PO BID or,
 
Ciprofloxacin* 500mg PO BID
 
	Until ANC >500/µL for 3 consecutive days	
Immunoglobulin replacement therapy	Hypogammaglobulinemia is common in CLL patients. Replacement with IVIG may be indicated for patients with IgG levels <500 and recurrent infections. However, some patients may benefit from IVIG replacement even if IgG is ≥500 if recurrent infections were common in their prior clinical history.			
*Adjust for renal function				

## 6.9 Duration of Therapy

Subjects will receive combined treatment until treatment discontinuation criteria is met. Upon meeting treatment discontinuation criteria, subjects will continue on the study in follow-up until study discontinuation criteria are met.

## 6.9.1 Criteria for the Discontinuation of Treatment

Subjects may withdraw from treatment or the study overall at any time at their request, or they may be withdrawn at the discretion of the Investigator or Sponsor for safety, behavioral reasons, or the inability of the subject to comply with the protocol-required schedule of study visits or procedures. In addition to the drug-specific discontinuation criteria listed in section 7, the following will result in treatment discontinuation:

• The subject requests to discontinue the study treatment and/or study procedures;

- Clinical deterioration that, in the opinion of the investigator, increases the risk to the subject;
- Confirmed disease progression based on iwCLL 2018 criteria (Section 7.5.3);
- Adverse events or intercurrent illness that in the opinion of the investigator warrants the subject's withdrawal from study treatment;
- Significant noncompliance with the protocol schedule or treatment administration in the opinion of the investigator;
- Pregnancy;

# 6.9.2 Criteria for the Discontinuation of Study

Subjects will be taken off study for the following:

- Completed study follow-up period;
- Participant or legally authorized representative requests to be fully withdrawn from the study;
- If, in the investigator's opinion, the continuation of the trial would be harmful to the subject's well-being;
- The subject is lost to follow-up;
- Screen failure;
- Death.

## 6.9.3 Withdrawal of consent

Subjects are free to withdraw from the study at any time without prejudice to further treatment. Subjects who withdraw consent for further participation in the study will not receive any further study medications or further study observation.

If a subject withdraws consent, they will be specifically asked if they are withdrawing consent to all further participation in the study including any further follow-up (e.g., survival contact telephone calls). Survival status may be obtained from public records for subjects who have withdrawn from any further follow-up contact.

## 6.9.4 Long Term Follow-Up for OS

Subjects that discontinue study treatment for any reason other than disease progression, must continue to have disease assessments until disease progression or the initiation of subsequent anticancer therapy per Section 4.5.

Upon discontinuation of study therapy, subjects will be followed for OS for 10 years from the date of study therapy initiation. Subjects or their legally authorized representatives will be contacted every 6 months (±14 days) during the first 5 years and then yearly (±28 days) during the following years thereafter until death, end of the study, or subject withdrawal of consent, whichever comes first. Survival and subsequent treatment status may be collected by public records, medical

records, or by contacting the subject or their legally authorized representative by phone. All efforts should be made to contact the subject at these time points. Refer below for Lost to Follow-Up guidelines.

# 6.9.4.1 Lost to Follow-Up

Subjects will be considered lost to follow-up only if no contact has been established by the time the study is completed, such that there is insufficient information to determine the subject's status at that time. Subjects who refuse to continue participation in the study, including telephone contact, should be documented as "withdrawal of consent" rather than "lost to follow-up." Investigators should document attempts to re-establish contact with missing subjects throughout the study period. If contact with a missing subject is re-established, the subject should not be considered lost to follow-up and evaluations should resume according to the protocol.

When a subject is lost to follow-up, site personnel should check hospital records, the subjects' current physician, and a publicly available death registry to obtain a current survival status.

In the event that the subject has actively withdrawn consent, the survival status of the subject can be obtained by site personnel from publicly available death.

# 7 STUDY ASSESSMENTS

Every effort should be made to ensure that the protocol-required tests and procedures are completed as described. However, it is anticipated that there may be circumstances, outside of the control of the Investigator that may make it unfeasible to perform the test. In these cases, the Investigator will take all steps necessary to ensure the safety and well-being of the subject. When a protocol-required test cannot be performed, the Investigator will document the reason for this and any corrective and preventive actions that he or she has taken to ensure that normal processes are adhered to as soon as possible.

## 7.1 General Assessments

## 7.1.1 Participant Consent

Before the initiation of any study procedures, all potential subjects or their legal representative must be fully informed of the risks and potential benefits of trial participation and demonstrate understanding. An informed consent document must be signed and dated by the participant or their legal representative indicating that they understand the risks and consent to participation and treatment on the study. The Principal Investigator or their appropriately trained and delegated study personnel conducting the informed consent discussion must also sign and date the document. A copy of the signed document should be provided to the subject.

Procedures, laboratory tests, or imaging performed as part of the standard of care prior to subject consent may contribute to the assessment of eligibility and/or screening procedures if performed during the screening period.

## 7.1.2 Medical History

The investigator or appropriately trained and delegated study personnel will collect medical history to the extent that supports the assessment of eligibility. The medical history will include any active

conditions and any conditions deemed to be clinically significant by the treating investigator. The use of symptom terms should be discouraged; if possible, terms describing the principal condition or syndrome should be used.

When collecting the initial medical history at screening, specific attention should be given to:

- Baseline symptoms
- A detailed history of prior cancers and cancer therapies including start and stop dates (duration of therapy), disease progression during or after therapy, discontinuation of therapies due to intolerability or any other serious illness, and length of remission.
- Past surgical, family, and social histories
- Past medical history as well as currently managed medical problems and their treatments
- ECOG performance status

When collecting medical history at subsequent study visits, specific attention should be given to:

- New symptoms related to potential adverse events
- Status of disease
- Management of previously documented adverse events and their current grade

#### 7.1.3 Cancer History

The oncologic history of the patient's CLL will be collected at the screening visit and will include:

- CLL status at initial diagnosis (if known)
  - Date of diagnosis
  - Age at diagnosis
  - Relevant laboratory measures including but not limited to complete blood count with differential, CLL FISH, beta 2 microglobulin, CLL NGS, IGHV mutational status, karyotype, CLL flow cytometry markers.
  - Rai and Binet stages
  - Presence of B-symptoms
- Time to first treatment defined as days from date of initial diagnosis to date of first treatment initiation
- Prior treatment regimens
  - Treatment name and type
  - Duration of therapy (if available, start and stop dates)
  - Best response on therapy
  - Reason for discontinuation
  - Sequence of therapies
  - Toxicities encountered while on each treatment regimen
  - Length of remission

• Current indication for treatment

## 7.1.4 Concomitant Medications

All medications currently being used by a study participant, regularly or as needed, must be reviewed and documented by the investigator or qualified designee. Specific attention should be given to medications with a protocol required washout as described in the exclusion criteria and any medication taken 28 days prior to cycle one day one. Refer to Section 6.7 for prohibited medications.

During protocol therapy, any medications taken by the patient or used to treat an adverse event will be documented in the subject's research chart and the corresponding eCRF. If a new anticancer therapy is initiated during study follow-up, the new therapy should also be recorded in the subject's research chart and corresponding eCRF.

# 7.1.5 CLL FISH Testing

It is required that all subjects have CLL FISH analysis after progression is noted from the most recent line of therapy and within 6 months of screening. Testing will be accepted from either peripheral blood and/or bone marrow samples. FISH probes should be directed to detect deletion 13q14, trisomy 12, deletion 11q22.3, and deletion 17p13. The CLL FISH testing must be confirmed by a Clinical Laboratory Improvement Amendments (CLIA) approved test. All FISH abnormalities should be recorded along with whether the deletion 13q14 was monoallelic or biallelic. If a patient has multiple FISH abnormalities, hierarchal FISH should be used.

## 7.1.6 Mutation Testing

It is required that all subjects have documentation of the necessary somatic mutations through local laboratory testing. Somatic mutation testing must be performed after progression is noted from the most recent line of therapy and within 6 months of screening. Testing will be accepted from either peripheral blood and/or bone marrow samples. At a minimum, the following somatic mutations should be tested: TP53, ATM, SF3B1, POT1, and XPO1. While not required, the following genes are strongly encouraged to be tested: NOTCH1, BIRC3, BRAF, KRAS, DDX3X, MYD88, and CXCR4. All detected gene mutations and their respective variant allele frequency (VAF) percentage should be recorded. The mutational status must be confirmed by a CLIA approved test.

## 7.2 Safety Assessments

## 7.2.1 Physical Examinations and Vital Signs

Subjects will have physical examinations to include major body systems, vital signs (blood pressure, heart rate, respiration rate, pulse oximetry, and body temperature), assessment of ECOG performance status (see Appendix 1), weight, and height at the time points described in the Schedule of Events. Particular attention should be paid to lymph nodes, spleen and liver. Documentation of lymph nodes should include location(s) and size (in centimeters) as noted in two orthogonal directions. Liver size should be documented as enlargement of the liver below the costavertebral angle as measured from the right mid-supraclavicular line in centimeters. Spleen

size should be documented as enlargement of the spleen below the costaverteral angle as measured from the left mid-supraclavicular line in centimeters.

## 7.2.2 Adverse Events

Adverse events experienced during trial participation will be collected per the Schedule of Events and Adverse Events Section. Each study participant will be questioned about the occurrence of adverse events in a non-leading manner. Should the treating investigator feel that the adverse event is attributed to study therapy, dose modification guidelines in the Dose Modification Section will be followed.

### 7.2.3 Laboratory Assessments

Samples for all laboratory assessments will be drawn at the time points indicated in the Schedule of Events and when clinically indicated. All safety laboratory analyses will be performed by the local laboratory for each study center. When applicable, all safety laboratory assessments must be reviewed by the treating investigator before study drug administration. When applicable, results from the pregnancy test must also be available for review before dosing.

Laboratory Assessments				
Complete Blood Count with Platelet Count and Differential	
 
White Blood Cell Count
 
Hemoglobin
 
Platelets
 
Manual or automated white blood cell count differential including:         
 
Absolute Neutrophil Count
 
Absolute Lymphocytes
 
 
 
			
Chemistry	
 
Absolute Lymphocytes
 
Complete Metabolic Panel         
 
Sodium
 
Potassium
 
Chloride
 
Carbon Dioxide
 
Alkaline Phosphatase
 
Aspartate Aminotransferase
 
Alanine Aminotransferase
 
Urea Nitrogen
 
Glucose
 
Creatinine
 
Calcium
 
Protein
 
Albumin
 
 
 
			
Tumor Lysis Syndrome	I otal Bilirubin     Lactate dehydrogenase			
(TLS)	

Phosphorus

Uric acid

			

Urine	24 hour urine
HIV and Hepatitis Serologies	
 
Hepatitis B Virus (HBV):         
 
Hepatitis B surface antigen (HBsAg)
 
Antibody to hepatitis B core antigen (anti-HBc)
 
Antibody to hepatitis B surface antigen (anti-HBs)
 
HBV DNA quantification (for subjects who are anti-HBs positive)
 
 
 
Hepatitis C Virus (HCV):         
 
Antibody to Hepatitis C (anti-HCV)
 
HCV-RNA (for subjects who are anti-HCV positive)
 
 
 
HIV         
 
Human Immunodeficiency Virus (HIV) Combo Antigen/Antibody (HIV-1/O/2)
 
 
 

Pregnancy	Beta-hCG Qualitative Urine or Serum

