 Pregnancy test (serum or urine) must be obtained at screening  $\leq$  3 days prior to C1D1 for all women of childbearing potential and as clinically indicated while on treatment.

 Must be conducted within 6 months of registration.

 If the subject has had successful testing in the past, this will be accepted and repeat *IGHV* mutational status will not be required.

 Should be performed after progression is noted from most recent line of therapy and within 6 months of screening and should include deletion 13q14, trisomy 12, deletion 11q22.3, deletion 17p13.

<sup>1 Screening procedures must be completed  $\leq$  42 days prior to C1D1 unless noted otherwise.

<sup>2 The end of treatment visit should occur when the patient discontinues treatment *for any reason*. This may be due but not limited to unacceptable toxicity from the combination therapy, patient/treating physician preference, progressive disease or completion of 18 cycles of combination therapy (whichever comes first). If this visit overlaps with a regularly scheduled visit, only the procedures listed in the calendar for the EOT visit will be performed. All end of treatment procedures should be completed  $\leq$  28 days after discontinuation of treatment.

 Should be performed after progression is noted from most recent line of therapy and within 6 months of screening. At a minimum, the following somatic mutations must be tested: *TP53, ATM, SF3B1, POT1* and *XPO1*. While not required, the following genes are strongly encouraged to be tested as well: *NOTCH1, BIRC3, BRAF, KRAS, DDX3X, MYD88 and CXCR4*.

 CLL MRD testing by flow cytometry should be performed on peripheral blood on C5D1, C9D1 and EOT.

 BM MRD testing by flow cytometry through a local lab should be performed on any BM aspirate obtained after screening. An additional aspirate sample should be collected and processed for correlative studies.

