### 4.4 Study Duration and Sample Size

With cohorts of 3 patients and possible early completion of the dose-escalation due to a DL accruing 12 patients, then the minimum time to accrue 4 cohorts is 4 months. Due to potential delays in patient enrollment and variability in dose escalation cohort size, the maximum enrollment time frame for the dose escalation portion is anticipated to be 24 months. Expansion at the RP2D is anticipated to be between 6-12 months as a portion of the dose escalation cohort treated at the RP2D will be rolled into the expansion cohort. Therefore, the total study duration is between 12-36 months, which is inclusive of the phase Ib and phase II durations.

On average, we expect 33 patients to be enrolled, assuming that 9 patients in the phase Ib portion will be treated at the MTD and rolled into the dose expansion phase. If the dose escalation portion enrolls patients only at the RP2D and all of these patients are rolled into the dose-expansion cohort, then the minimum number of patients required would be 24 for the entire trial. The maximum number of patients required would be 39 assuming that only 3 patients roll over from the dose escalation to the dose expansion.

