# 5 STUDY POPULATION

Potential study participants must meet all inclusion criteria and no exclusion criteria to be deemed eligible for trial participation. To ensure subject safety, all subjects must be deemed eligible at the time of study registration and must continue to meet eligibility criteria up to cycle one day one dosing. This eligibility checklist is used to determine subject eligibility and will be filed with the enrolling investigator's signature in the subject research chart.

- 5.1 Inclusion Criteria
- 5.1.1 \_\_\_\_\_ Diagnosis of CLL according to the NCI/IWCLL criteria.

This includes previous documentation of:

a. Biopsy-proven small lymphocytic lymphoma/CLL

# 

- b. Diagnosis of CLL according to the NCI/IWCLL criteria as evidenced by all of the following:
  - 1. Peripheral blood monoclonal B cell population of greater than  $5x10^{9}/L$

- 2. Immunophenotype consistent with CLL defined as:
  - The predominant population of lymphocytes share both B cell antigens [CD19, CD20 (typically dim expression), or CD23] as well as CD5 in the absence of other pan-T-cell markers (CD3, CD2, etc).
  - Clonality as evidenced by κ or λ light chain restriction (typically dim immunoglobulin expression)
- c. Negative FISH analysis for t(11;14)(IgH/CCND1) on peripheral blood or tissue biopsy (e.g. marrow aspirate), or negative immunohistochemical stains for cyclin D1 on involved tissue biopsy (e.g. marrow aspirate or lymph node biopsy).

5.1.2 \_\_\_\_\_ Repeat testing of somatic mutations and FISH analysis must be performed by a CLIA certified laboratory after progression is noted from most recent line of therapy and within 6 months of screening. Primary CLL cells must harbor at least one of these abnormalities:

- Somatic gene mutation testing shows mutation(s) in TP53, ATM, SF3B1, XPO1 and/or POT1
- Cytogenetic FISH analysis shows deletion 17p13 and/or deletion 11q22.3

5.1.3 \_\_\_\_\_ Relapsed or refractory after at least 2 prior lines of therapy, and in the opinion of the treating Investigator are either not eligible for other approved therapies or no approved therapies are expected to have sustained therapeutic benefit.

5.1.4 \_\_\_\_\_ Patient in need of treatment or change in treatment per iwCLL criteria.

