- 5.1.9 \_\_\_\_\_ Able to adhere to study visit schedule and other protocol requirements
- 5.1.10 \_\_\_\_\_ Patients must be able to swallow capsules

5.1.11 \_\_\_\_\_ Patients must be able to receive xanthine oxidase inhibitor and/or rasburicase for tumor lysis syndrome prophylaxis.

5.1.12 \_\_\_\_\_ Patients with a history of hepatitis B (surface antigen or core antibody-positive and PCR positive) must take lamivudine or equivalent drug during study therapy and for one year after completion of all therapy. Patients on IVIG who are core antibody-positive but PCR negative are not mandated to take prophylaxis.

5.1.13 \_\_\_\_\_ Patients who are HIV+ are eligible under the following circumstances:

- Undetectable HIV viral load (laboratory value obtained within the last 6 months prior to enrollment)
- CD4 count ≥200 (laboratory value obtained within the last 6 months prior to enrollment)
- Actively taking antiretroviral therapy (ART)
- Current ART therapy cannot have significant interactions with RP-3500 or Olaparib (Refer to Appendix 5). If current medications do interact, patients should receive alternative ART.

5.1.14 \_\_\_\_ Recovery to baseline or  $\leq$  Grade 1 CTCAE v5.0 from toxicities related to any prior cancer therapy, unless considered clinically not significant by the treating investigator.

5.1.15 \_\_\_\_\_ Female patients capable of reproduction or males who have partners capable of reproduction must agree to the use of an effective contraceptive method during the course of the study and for 6 months following the completion of their last treatment.

5.1.16 \_\_\_\_ Females of childbearing potential must have a negative serum  $\beta$ -Hcg pregnancy test result within 3 days of the first study dose. Female patients who are surgically sterilized or who are >45 years old and have not experienced menses for >2 years may have  $\beta$ -Hcg pregnancy test waived.

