# 5.3 Registration

Subjects must meet all of the eligibility requirements before registration. Study-related screening procedures can only begin once the subject has signed the consent form. Subjects must not begin protocol treatment prior to registration.

Treatment should start within 14 days after registration.

To register eligible subjects on study, complete a Clinical Trials Office Subject Registration Form and submit to [contact].

For sites outside of Huntsman Cancer Institute, submit registration forms to [contact]

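### The HBV DNA test in Section 7.2.3 is triggered by anti-HBs, a marker that inclusion criterion 5.1.12 does not use, so some patients whose antiviral treatment depends on PCR have no PCR scheduled.

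*Combined protocol and SAP*

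**What the plan says.** Criterion 5.1.12 (Section 5.1) sets the treatment rule: "Patients with a history of hepatitis B (surface antigen or core antibody-positive and PCR positive) must take lamivudine or equivalent drug during study therapy". The obligation continues for one year after all therapy ends. A second sentence of the criterion releases patients on IVIG who are anti-HBc positive and PCR negative. Neither sentence mentions anti-HBs.

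The hepatitis row of the laboratory table in Section 7.2.3 lists HBsAg, "Antibody to hepatitis B core antigen (anti-HBc" and anti-HBs for every patient. It then adds "HBV DNA quantification (for subjects who are anti-HBs positive". The HCV line in the same row reads "HCV-RNA (for subjects who are anti-HCV positive".

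Footnote 14 to the Schedule of Events (Section 1.3) gives only a time window for the serologies: "Must be conducted within 6 months of registration". No other part of the document orders HBV DNA. Section 7.2.3 also allows samples outside the schedule when there is a clinical reason.

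On timing, Section 5 states that "all subjects must be deemed eligible at the time of study registration", and Section 5.3 that "Subjects must meet all of the eligibility requirements before registration".

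**The concern.** The test trigger and the treatment rule use different markers. The table draws both markers that 5.1.12 relies on, yet neither leads to a PCR. A positive anti-HBs, which 5.1.12 ignores, does. By contrast, the HCV line ties the RNA test to the HCV antibody itself, so the HBV line may be a slip for anti-HBc. Sites nevertheless order tests from the table as it stands.

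The patient at risk is anti-HBc positive, anti-HBs negative and carrying HBV DNA. A site following the table literally would have no PCR result and no instruction to obtain one. That patient could start treatment without the antiviral that 5.1.12 makes mandatory. Section 6.8 describes CLL patients as immunocompromised and anticipates leukopenia and neutropenia on this combination.

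The endpoints, sample size and analysis are not directly affected. The problem is an inconsistency between two operative safety instructions.

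**Working it through.** **Inputs.** The treatment rule comes from 5.1.12 and the test trigger from the table in 7.2.3. Section 4.4 gives a minimum of 24 patients and a maximum of 39 ("The maximum number of patients required would be 39"). The documents give no prevalence for any serology pattern, so the prevalences in step 3 are assumptions. The plan states no figure of its own to reproduce here.

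**Step 1: the two readings of 5.1.12.** The PCR condition in its parenthesis can attach in two ways.

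- Reading A: (HBsAg positive or anti-HBc positive) and PCR positive. PCR decides whenever either marker is positive.
- Reading B: HBsAg positive, or (anti-HBc positive and PCR positive). HBsAg alone mandates treatment, so PCR decides only when HBsAg is negative and anti-HBc is positive.

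**Step 2: all eight patterns against the trigger.** The table orders HBV DNA if and only if anti-HBs is positive.

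| HBsAg | anti-HBc | anti-HBs | HBV DNA ordered | PCR decides, A | PCR decides, B | Missed |
|---|---|---|---|---|---|---|
| − | − | − | no | no | no | – |
| − | − | + | yes | no | no | – |
| − | + | − | no | yes | yes | A and B |
| − | + | + | yes | yes | yes | – |
| + | − | − | no | yes | no | A |
| + | − | + | yes | yes | no | – |
| + | + | − | no | yes | no | A |
| + | + | + | yes | yes | no | – |

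On reading A, PCR decides in 6 patterns and 3 are missed, all anti-HBs negative. On reading B, PCR decides in 2 and 1 is missed. The pattern HBsAg−/anti-HBc+/anti-HBs− is missed on both. Patients positive for both anti-HBc and anti-HBs are covered. In the second row the table orders a PCR that 5.1.12 does not use.

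**Step 3: how many patients.** Let p be the assumed proportion with the pattern missed on both readings, and n the number enrolled. The expected number is n × p, and the chance of at least one is 1 − (1 − p)^n.

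| p (assumed) | n × p, n = 24 | n × p, n = 39 | P(at least one), n = 24 | P(at least one), n = 39 |
|---|---|---|---|---|
| 0.01 | 0.24 | 0.39 | 1 − 0.99^24 = 21.4% | 1 − 0.99^39 = 32.4% |
| 0.02 | 0.48 | 0.78 | 1 − 0.98^24 = 38.4% | 1 − 0.98^39 = 54.5% |
| 0.05 | 1.20 | 1.95 | 1 − 0.95^24 = 70.8% | 1 − 0.95^39 = 86.5% |

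These are chances of meeting the serology pattern, not of harm. Harm also requires that the patient is PCR positive, that nobody orders the PCR outside the table, and that no antiviral is given. The documents allow none of these to be quantified.

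**Step 4: the corrected trigger.** If HBV DNA is ordered whenever HBsAg or anti-HBc is positive, the six patterns in which PCR decides on reading A are all tested. They include the two of reading B, so the number missed is 0 on either reading.

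**The case against.** The strongest reply is that 5.1.12 protects the patient by itself. It is an eligibility criterion worded in terms of PCR. An investigator must sign the checklist before registration with the anti-HBc result in hand, and Section 7.2.3 permits unscheduled tests. An attentive investigator would see that the PCR is missing and order it. That is a real safeguard, and it is why the test should be called unscheduled rather than prohibited. It does not correct the trigger: the sign-off needs the result but does not order it, and the table's explicit condition implies that an anti-HBs-negative patient needs no HBV DNA.

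A second reply concerns the IVIG sentence. On readings A and B, a patient who is HBsAg negative, anti-HBc positive and PCR negative is already outside the mandate, so the IVIG exemption does no work. A reading that gave it a purpose would treat all anti-HBc-positive patients by default and release only PCR-negative patients on IVIG. A missing PCR would then lead to treatment, not omission. This shows that 5.1.12 is loosely drafted, but the reading contradicts the criterion's own requirement that the patient be PCR positive.

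Third, liver chemistry is scheduled at the study visits, and Section 8.3.2 names viral hepatitis among the causes to exclude when liver tests rise. That may limit undetected harm, but it is monitoring after the event and does not replace prophylaxis.

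Finally, the prevalences are assumed, and the percentages do not measure harm. Both points stand, and the conclusion does not depend on them.

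**Conclusion.** The concern holds. Followed literally, the table withholds the PCR result that a mandatory safety rule needs, for 3 of 6 relevant serology patterns on one reading of 5.1.12 and 1 of 2 on the other. The HBsAg-negative, anti-HBc-positive, anti-HBs-negative patient is missed on both. This follows from the text alone and needs no assumption about prevalence.

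The number of patients is probably small: about 0.2 to 2.0 expected across assumed prevalences of 1% to 5% and 24 to 39 patients. The point should be fixed because of the possible consequence for an individual patient and the ease of correction. The IVIG exemption is not part of the problem: without a PCR it cannot be used, which errs toward treatment.

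**What to change.** In the hepatitis row of the Section 7.2.3 table, change the condition for HBV DNA quantification to: *for subjects who are HBsAg positive or anti-HBc positive*. Anti-HBs may be kept as an additional trigger, so no planned test has to be dropped. State in the same row that the result must be available before registration. This largely restates Sections 5 and 5.3, but puts the requirement where sites order the test. The prophylaxis rule in 5.1.12 can stay as written, because the new trigger works on both readings.

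The cost is one line of text. At the assumed prevalences it adds about 0 to 2 PCR tests for the pattern missed on both readings, plus one for any patient who is HBsAg positive and anti-HBs negative.
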